## 7.3 Center Pooling

Although data for this registry will be collected from multiple centers, no center pooling analyses are planned.

## 7.4 Handling of Missing, Unused, and Spurious Data and Dropouts

Every effort will be undertaken to minimize missing, unused and spurious data and dropouts. Unless otherwise specified, no statistical techniques will be used to impute missing data. The number of subjects included in each analysis will be reported so that the reader can assess the potential impact of missing data.

In the case of partial dates, if only the month and year are known, the event or assessment will be analyzed as if it occurred on the 15th of that month. If only the year is known, the event or assessment will be analyzed as if it occurred on June 30th of that year. These resolutions of partial dates are subject to the restrictions that events must occur no earlier than the procedure date or after study exit.

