#### 7.1.3 Analysis Sets

There are three analysis sets defined for this study. Analysis sets used for each objective are defined in the corresponding objective section. The primary analysis set is the Successfully Implanted analysis set.

- Enrolled analysis set: Composed of all subjects who signed the Patient Informed Consent Form. Time zero begins on the date of informed consent.
- Attempted Implant analysis set (AT): Composed of all enrolled subjects who were attempted for a Profile 3D™ or CG Future® Annuloplasty system implantation. A subject with one or more attempts of the Medtronic study device recorded on the procedure case report form (CRF) is considered as implant attempted. Time zero begins on the date of the first attempted procedure.
- Successfully Implanted analysis set (IMP): Composed of all AT subjects who had either a Profile 3D™ or CG Future® Annuloplasty system implanted successfully. Time zero begins on the date of implant procedure.

All data collected from enrolled, attempted implant, and successfully implanted subjects will be utilized in the analyses as appropriate. Analyses of the primary and secondary endpoints will be descriptive, and no statistical hypothesis tests will be performed.

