### 7.2 General Methodology

Descriptive statistics will be used to report study data. For continuous variables (e.g. age), the mean, median, standard deviation, minimum, maximum, and first and third quartiles will be presented. For categorical variables, the number and percentage of subjects in the category of interest will be presented. For time to event data, Kaplan-Meier analyses of event or event-free rates at discharge, 6 and 12 months will be presented. For these analyses, the time points will correspond to 7 days, 183 days and 365 days post implantation respectively. At each time point with data, the product limit estimate of the event or event-free rates, and the loglog transformed 95% confidence interval using the Peto standard error will be presented. For subjects without an event, the date of censoring will be the latest date of all follow-up visits (including phone and/or mail correspondence), assessments, events (including death) and study exits. For subjects whose exit reason is lost to follow-up, the last follow-up date will be the latest date of the follow-up visits (including phone and/or mail correspondence), assessments and events.

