**7.9.7 Secondary Endpoint #5**

Mitral valve re-intervention at discharge, 6 and 12 months post procedure.

Hypothesis/Decision criteria:

No specific hypotheses or pass/fail criteria have been set. The analysis will be descriptive and no statistical hypothesis test will be performed.

Endpoint Definition/Parameters to Be Estimated:

Mitral valve re-intervention event rate estimate will be provided at discharge, 6 and 12 months post procedure.

Data Collection and Analysis Dataset:

Data will be collected on a RE-INTERVENTION (RE-OP) CRF.

This objective will be analyzed for the Successfully Implanted (IMP) cohort.

Analysis Method:

A Kaplan-Meier analysis will be performed.

The number and percentage of subjects with mitral valve re-intervention post implant on or prior to discharge will also be presented, as described in section 7.2.

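### SAP 7.4 can place a poorly dated event from the calendar year of surgery on day 0, and so in the day-7 rate, because imputed dates are not bounded by event-free contacts

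*Combined protocol and SAP*

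**What the plan says.** SAP 7.4 gives two rules for incomplete dates. For a known month, "if only the month and year are known, the event or assessment will be analyzed as if it occurred on the 15th of that month". For a known year, "If only the year is known, the event or assessment will be analyzed as if it occurred on June 30th of that year". One limit follows: "These resolutions of partial dates are subject to the restrictions that events must occur no earlier than the procedure date or after study exit". The SAP does not say how a date outside that range is to be reset. Neither document limits an imputed date by what later contacts showed.

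Three other statements fix where such an event lands. In SAP 7.1.3, for the successfully implanted set, "Time zero begins on the date of implant procedure". In SAP 7.2, "Kaplan-Meier analyses of event or event-free rates at discharge, 6 and 12 months will be presented", and "the time points will correspond to 7 days, 183 days and 365 days post implantation respectively". So the discharge rate is read at day 7.

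The endpoint sections differ in what they ask for at discharge:

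- Re-intervention (7.9.7): "Mitral valve re-intervention event rate estimate will be provided at discharge, 6 and 12 months post procedure". A simple count up to discharge is also required.
- New-onset atrial fibrillation (7.9.9): evaluated at discharge among other visits, and analysed by Kaplan-Meier.
- Heart failure hospitalization (7.9.6) and stroke (7.9.8): 6 and 12 months.
- All-cause mortality (7.9.2): 12 months only.

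**The concern.** A fixed calendar date takes no account of when the subject was operated on. When 30 June comes before surgery, the only stated limit that can act is the procedure date, and the natural way to apply it is to move the event to day 0. An event that may have occurred months later is then counted as perioperative.

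The rule also ignores information the study holds. Take a subject operated on in May, seen free of the event on 20 July, whose event is recorded only by that year. The event is dated 30 June, which the study's own visit record contradicts.

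Early rates after valve surgery rest on few events, so one or two misplaced ones can show. At stake is the discharge estimate, mainly for re-intervention and new-onset atrial fibrillation.

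**Working it through.** The plan states no figure to reproduce here, so the check applies the rule to calendar dates.

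**Inputs from the documents.** Enrollment starts in July 2017 and lasts about 20 months (protocol 6.1), taken as 1 July 2017 to 28 February 2019, or 608 days. Day 0 is the implant date. Rates are read at days 7, 183 and 365. The sample size is 200.

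**Assumptions.** An out-of-range date is moved to the nearest permitted date. Procedures are uniform over enrollment. Events fall within days 0 to 365.

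**Rule.** Imputed day = max(30 June of the event year, procedure date) − procedure date.

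| Operation | Event in same year: imputed day | Latest possible true day | Event in next year: imputed day |
|---|---|---|---|
| 1 July 2017 | 0 | 183 | 364 |
| 1 August 2017 | 0 | 152 | 333 |
| 1 October 2017 | 0 | 91 | 272 |
| 31 December 2017 | 0 | 0 | 181 |

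Only events in the calendar year of the operation go to day 0. Operations on 23 to 30 June have nearly the same problem: same-year events land on days 7 to 0. July to December covers 2 × 184 = 368 of 608 enrollment days (61%).

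**Month-only dates.** Surgery on the 15th with an event on the 31st gives day 0 against a true day 16. Surgery on the 8th gives day 7 against a true day of up to 23. The error is at most 16 days in both cases.

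**Share of year-only events counted by day 7**, over all procedure days and event days. The midpoint without contact bounds uses only the known year, the procedure date and study exit (taken as day 365). The bounded midpoint assumes contacts at days 7, 150 and 365.

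| Assumed event times | True | SAP rule | Midpoint, contact bounds |
|---|---|---|---|
| Uniform over 12 months | 2.2% | 16.0% | 2.2% |
| Exponential, mean 60 days | 12.5% | 43% | 12.5% |

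The bounded rule recovers the true share by construction, because the day-7 contact separates early from late events. Without contact bounds, the midpoint gives about 0.6% in the early-clustered case against a true 12.5%.

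Mean absolute dating error, SAP rule to bounded midpoint: 76 to 39 days (uniform) and 68 to 30 days (early-clustered). The unbounded midpoint gives about 62 and 70 days. With the same contacts, the SAP rule dates about 24% (uniform) or 37% (early-clustered) of year-only events at or before a contact at which the subject was event-free.

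**Size in the reported rate.** One event wrongly counted by day 7 adds 1/200 = 0.5 points with 200 at risk. Averaged over where a year-only event might fall, each adds (16.0% − 2.2%)/200 = 0.07 points (uniform) or (43% − 12.5%)/200 = 0.15 points (early-clustered).

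**The case against.** The strongest reply is that year-only dates will be rare. The protocol asks for prompt reporting of serious adverse events, with 24 hours recommended (11.2). It collects these events at every visit (9.9) and checks data against source documents with queries (15.2.3). A re-operation or stroke known only by its year would be exceptional. The percentages above are shares of year-only events, not of all events. This stands, and it limits the absolute bias.

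Two further replies also stand. The move to day 0 is inferred, because SAP 7.4 states a restriction without saying how to enforce it. Exposure at day 7 is narrow: only the re-intervention section names a discharge rate, atrial fibrillation is evaluated at discharge, and the other endpoints reach day 7 only through the general sentence in SAP 7.2.

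A reader might infer more than the documents support:

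- **That every year-only event after a July-to-December operation goes to day 0.** Events in the following year land between days 181 and 364. With uniform timing these are about 75% of year-only events in those operations.
- **That the 12-month mortality endpoint is distorted by this shift.** An event moved to day 0 truly occurred by day 183 (day 184 for an operation on 30 June itself), so it does not cross day 365.
- **That a baseline echo could be redated to after surgery**, since the restriction mentions events and not assessments. Echo data are collected by visit, and nothing says that baseline status is assigned from an imputed date, so no consequence is shown.

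None of this answers the core point: the rule can give a date that the study's own contacts rule out.

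**Conclusion.** The point holds and is minor. On the natural reading of SAP 7.4, a year-only event in the calendar year of an operation after 30 June is placed on day 0, up to 183 days too early, and nothing stops an imputed date from preceding a documented event-free contact. The likely effect is an inflated day-7 rate: explicit for re-intervention, probable for new-onset atrial fibrillation, and for other endpoints only if the general reporting in SAP 7.2 is followed.

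The shares of 16% and 43% depend on the assumed accrual and event times. The absolute effect depends on the number of partial dates, which the documents do not give. With only a few, the bias is a fraction of a percentage point, up to 0.5 points for each event actually misplaced.

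**What to change.** In SAP 7.4, replace the fixed dates with the midpoint of the feasible interval:

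- **Lower bound:** the latest of the procedure date, the last contact documented event-free, and the first day of the known month or year.
- **Upper bound:** the earliest of study exit, the first contact documenting the event, and the last day of the known month or year.

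Report the number of imputed dates for each endpoint.

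The contact bounds are essential. A midpoint without them would replace an overcount of early events with an undercount. The midpoint remains approximate where a long interval spans a reporting time such as day 183, which is one more reason to show the count of imputed dates.

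The cost is a few sentences in the SAP and a small change to the date program. No new data are needed, since SAP 7.2 already uses follow-up contact dates for censoring.

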## 7.5 Adjustments for Multiple Comparisons

No multiple comparisons/multiplicity adjustments will be made.

## 7.6 Demographic and Other Baseline Characteristics

Demographics and baseline characteristics will be summarized for the Enrolled and Successfully Implanted analysis sets. Continuous variables will be summarized with means, medians, standard deviations, minimums, maximums, and first and third quartiles. Categorical variables will be summarized with frequencies and percentages.

## 7.7 Treatment Characteristics

Procedural data will be summarized for the Attempted Implant and Successfully Implanted analysis sets. Continuous variables will be summarized with means, medians, standard deviations, minimums, maximums, and first and third quartiles. Categorical variables will be summarized with frequencies and percentages.

## 7.8 Interim Analyses

An interim summary of the data is planned when all enrolled and successfully implanted subjects have had the opportunity to be followed through the discharge visit. This is an observational study. No statistical hypothesis tests will be performed, and there are no pass/fail criteria for the results of this study.

## 7.9 Evaluation of Objectives

### 7.9.1 Primary Endpoint #1

Improvement in mitral valve regurgitation (MR) (grade) at 12 months post procedure.

Hypothesis/Decision criteria:

No specific hypotheses or pass/fail criteria have been set. The analysis will be descriptive and no statistical hypothesis test will be performed.

**Endpoint Definition/Parameters to Be Estimated:**

Mitral valve function will be based on site echocardiographic recordings. The parameter to be estimated is the grade of mitral valve regurgitation using echo, in subjects at baseline and 12 months post procedure. The grades of MR, 0-4, will correspond to the ASE guidelines (as described in Table 1 in CIP) ranging from no MR, Mild MR, Moderate MR, Moderate-to-Severe MR and Severe MR.

**Data Collection and Analysis Dataset:**

Data will be collected on an ECHOCARDIOGRAM (CV) CRF.

This objective will be analyzed for the Successfully Implanted (IMP) cohort, and for the IMP subjects with CG Future Band, CG Future Ring and Profile 3D Ring respectively. IMP subjects having available MR collection at both baseline and 12 months post procedure will be included in the analysis.

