**Table 3: NYHA functional class definitions**

Classification	Description
Class I	Patients with cardiac disease, but without resulting limitations of physical activity. Ordinary physical activity does not cause undue fatigue, palpitation, dyspnea, or anginal pain.
Class II	Patients with cardiac disease resulting in slight limitation of physical activity. Patients are comfortable at rest. Ordinary physical activity results in fatigue, palpitation, dyspnea, or anginal pain.
Class III	Patients with cardiac disease resulting in marked limitation of physical activity. Patients are comfortable at rest. Less than ordinary physical activity causes fatigue, palpitation, dyspnea, or anginal pain.
Class IV	Patients with cardiac disease resulting in inability to perform any physical activity without discomfort. Symptoms of cardiac insufficiency or of the angina syndrome may be present even at rest. If any physical activity is undertaken, discomfort is increased.

- Hospitalization for Heart Failure at 6 months and at 12 months post procedure

Hospitalizations for Heart Failure are defined as a non-elective hospital admission for signs and symptoms related to heart failure that results in a one-night stay (i.e., where the admission date and the discharge date differ by at least one calendar day). For the purpose of the protocol, overnight stays at nursing home facilities or extended care facilities do not meet the protocol definition of hospitalization. The occurrence of hospitalization for heart failure will be evaluated at 6 months and 12 months post procedure.

- Mitral valve re-intervention at discharge, 6 months and at 12 months post procedure

Following the completion of the procedure, defined as the subject leaving the operating theater with an implanted Profile 3D™ or CG Future® annuloplasty system, any surgical or percutaneous interventional catheter procedure that repairs, otherwise alters or adjusts, or replaces the previously implanted annuloplasty system will be termed re-intervention. In addition to surgical

reoperations, enzymatic, balloon dilatation, interventional manipulation, repositioning, or retrieval, and other catheter-based interventions for valve-related complications are also considered re-interventions. The re-intervention rate will be evaluated at discharge, 6 months and 12 months post procedure.

- Stroke at 6 months and at 12 months post procedure

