## 9.11. Subject Withdrawal or Discontinuation

All subjects will be encouraged to remain in the registry through the last follow-up visit at 12 months. Subjects who discontinue participation prematurely after attempted implant will be included in the analysis of results (as appropriate) but they will not be replaced in the enrollment of total study subjects. If a study subject is discontinued from the study early, the reason for discontinuation should be documented in the subject file and a Study Exit eCRF must be completed. If discontinuation is because of safety concerns, the subject shall be asked to be followed for collection of ongoing safety data outside the study. Any data collected after the exit date will not be analyzed as part of the study.

In case the subject undergoes device explant, the subject will be exited from the study.

The subjects will be exited from the study following their 12 month follow up visit. This 12 month visit will be primarily conducted via in-office visit and has a window period of additional 1 month, up to day 395 post implant. All adverse event information will be collected and reported during this follow up visit, as per timelines described above in section 11.2; subjects will be considered exited from the study on completion of their 12 month visit or when they are considered lost to follow up (after three failed attempts are made to contact the subjects).

The investigating site and Sponsor will make every effort to have all subjects complete the follow up visit schedule. A subject will not be considered lost-to-follow-up unless all efforts to obtain compliance are unsuccessful. At a minimum, the effort to obtain follow-up information must include three attempts to make contact via telephone and if contact via phone is not successful, a traceable letter from the Investigator must be sent to the subject's last known address. Should both telephone and mail efforts to contact the subject be unsuccessful, the subject's primary physician should be contacted. Subjects will then be deemed lost to follow up. All contact efforts to obtain follow-up must be documented in the subject's medical records.

If a subject discontinues the study at any time, is withdrawn from the study early, or completes all protocol required follow-up they should then be followed per the local standard of care for their condition.

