**Analysis Method:**

For each subject with paired data, the change from baseline (improved, no change, worsened) will be evaluated at 12 months. This primary endpoint of improvement in MR (grade) will be presented with frequencies and percentages of subjects with improved MR at 12 months. Two-sided 95% exact binomial confidence intervals of the percent of subjects overall and in each of the three subgroups with improved MR at 12 months will also be reported.

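### The primary MR percentage has no rule for re-intervention: a repair rescued with the device in place can count as improved, and explanted subjects leave the denominator

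*Combined protocol and SAP*

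**What the plan says.** SAP 7.9.1 sets one condition for entering the 12-month MR analysis beyond successful implantation: "IMP subjects having available MR collection at both baseline and 12 months post procedure will be included in the analysis". Classification follows from the two grades: "For each subject with paired data, the change from baseline (improved, no change, worsened) will be evaluated at 12 months". The result is a percentage improved, with "Two-sided 95% exact binomial confidence intervals of the percent of subjects overall and in each of the three subgroups with improved MR". CIP 13.5 gives the same paired rule.

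CIP 5.2.2 defines re-intervention widely. After the subject leaves the operating theatre, "any surgical or percutaneous interventional catheter procedure that repairs, otherwise alters or adjusts, or replaces the previously implanted annuloplasty system will be termed re-intervention"; balloon dilatation, repositioning and other catheter procedures for valve-related complications are added. Several of these leave the device in place.

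CIP 9.11 has an exit rule for explant only: "In case the subject undergoes device explant, the subject will be exited from the study". It adds: "Any data collected after the exit date will not be analyzed as part of the study". It has no exit rule for re-intervention without explant.

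Re-intervention is its own secondary endpoint in SAP 7.9.7: "Mitral valve re-intervention event rate estimate will be provided at discharge, 6 and 12 months post procedure". On the source, that section says: "Data will be collected on a RE-INTERVENTION (RE-OP) CRF". Nothing links it to the MR result.

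**The concern.** The primary objective concerns the clinical outcomes of the Profile 3D and CG Future systems, so a reader will take the percentage improved at 12 months as a description of those repairs. Under the stated rules, a repair that failed through residual or recurrent MR, and was then rescued in place, can appear in the numerator as a success. A repair that failed and led to explant appears nowhere in the percentage.

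The study makes no hypothesis test and has no pass/fail criterion. The percentage and its interval are therefore the whole result for this endpoint, and what counts as improved needs to be explicit. The CIP background (4.1) and SAP 3 both say that repair in the largely rheumatic local population has a higher failure rate, so failed repairs are a foreseeable event here.

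**Working it through.** **Text check.**

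1. Can a re-intervention occur without explant? Yes. The CIP 5.2.2 definition includes procedures that repair, alter or adjust the implanted system.
2. Does that subject stay in follow-up? Yes. CIP 9.11 exits on explant and is silent on other re-interventions.
3. Does the subject enter the primary analysis? Yes, if both grades exist (SAP 7.9.1).
4. How is the subject scored? As improved if the 12-month grade is below baseline; otherwise as no change or worsened. There is no category for re-intervention.
5. What happens to an explanted subject? Exit, no analysable 12-month echo, no pair, and so no place in the denominator.
6. Is there a correcting rule elsewhere? I looked in CIP 5.2.1 and 13.5 and in SAP 7.2, 7.4, 7.9.4 and 7.12. None excludes, reclassifies or flags these subjects. By contrast, SAP 7.9.5 carries death as its own category for NYHA class.

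SAP 7.9.4 has the same gap at discharge and 3-6 months. Its inclusion wording differs, since it lists MR at baseline, discharge and 3-6 months together.

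**Size.** The plan gives no expected improvement rate, re-intervention rate or device split, and N = 200 is stated as not statistically derived. There is no figure to reproduce, and every input below is assumed.

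Let n be the paired subjects, x those scored improved, k those among x who had a re-intervention for MR with the device left in place, and e those explanted before the visit. Intervals are exact binomial (Clopper-Pearson).

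- As written: x/n
- Rescued subjects rescored: (x − k)/n, a shift of k/n
- Explants also restored: (x − k)/(n + e)

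With n = 180 and x = 162:

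| k | e | Fraction | Percent (95% CI) |
|---|---|---|---|
| 0 | 0 | 162/180 | 90.0 (84.7 to 94.0) |
| 2 | 0 | 160/180 | 88.9 (83.4 to 93.1) |
| 4 | 0 | 158/180 | 87.8 (82.1 to 92.2) |
| 6 | 0 | 156/180 | 86.7 (80.8 to 91.3) |
| 4 | 4 | 158/184 | 85.9 (80.0 to 90.6) |

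The shift from rescoring alone is 2/180 = 1.1 to 6/180 = 3.3 points.

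**Why explants must be covered too.** Suppose 10 of 200 repairs fail and 170 of the other 190 subjects improve.

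- All 10 rescued in place and all below baseline at 12 months: the plan reports 180/200 = 90.0% (85.0 to 93.8).
- All 10 explanted: the plan reports 170/190 = 89.5% (84.2 to 93.5).
- Failures kept in and scored as not improved: 170/200 = 85.0% (79.3 to 89.6).

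The first two figures are close together and both are well above the third. A rule that only rescored the in-place rescues would leave the explant route open.

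**Subgroups.** The shift is k/n, so at a given re-intervention rate its expected size is the same in a device subgroup as overall. Only the weight of one subject changes: 1/180 = 0.6 points overall against 1/60 = 1.7 points in an assumed subgroup of 60.

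**The case against.** The strongest reply is that the endpoint can be read as it stands: MR grade at 12 months against baseline, whatever happened in between, in a non-interventional registry with no test. That is a legitimate descriptive quantity, and re-intervention is reported in the open under SAP 7.9.7. This stands, and it is why the as-observed percentage should be kept. It does not settle the matter. The plan never says that this is the reading, and a separate re-intervention curve does not tell the reader how many of the improved subjects needed a second procedure.

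Three stronger readings are tempting, and the documents do not support them.

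- A reader might infer that every re-intervention marks an MR failure and explains the later grade. The definition also covers other valve-related complications, and CIP 10.1 lists stenosis, hemolysis and thrombosis among others. Such a subject may owe the lower grade to the original ring or band.
- A reader might infer that every re-intervened subject is counted as a success. One whose 12-month grade is not below baseline is scored as no change or worsened.
- A reader might infer a larger bias in the device subgroups. The arithmetic shows greater variability there, not greater expected bias.

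It is also fair to say that the true count may be small. In the illustration, the 1.1 to 3.3 point shift lies within the as-written interval. The remark about higher failure in rheumatic disease says nothing on how often a failed repair is treated with the device left in place.

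**Conclusion.** The gap is real and worth closing. As written, a repair rescued in place for residual or recurrent MR can enter the primary percentage as improved, and an explanted subject drops out of it. Where the re-intervention was MR-related, both routes can make the percentage look more favourable as a description of the original repair.

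The amount cannot be derived from the documents. The range of 1.1 to 3.3 points assumes 180 paired subjects, 162 scored improved, and 2 to 6 MR-related rescues, all of them in the numerator. With four explants added to four rescues, the difference is 90.0 − 85.9 = 4.1 points. No hypothesis test is affected. The conclusion concerns what the headline describes and what should stand beside it; it does not make the observed percentage invalid.

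**What to change.** In SAP 7.9.1, and in 7.9.4 for the discharge and 3-6 month echoes:

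1. Keep the as-observed percentage and state that it is regardless of re-intervention.
2. Using the RE-OP CRF, flag subjects with a mitral re-intervention before the echo in question, and show the reason as MR-related or other.
3. Add one supplementary percentage with an exact 95% interval, overall and by device. Score as not improved the subjects with an MR-related re-intervention before the echo and the subjects explanted before the visit, and keep the explanted subjects in the denominator.

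The cost is SAP wording and one extra row per MR table; no visit or procedure changes. The Kaplan-Meier analysis in SAP 7.9.7 already needs the re-intervention date. The documents do not show whether the RE-OP form records the reason; if it does not, the reason would have to come from the AE CRF or a site query. The supplementary figure will be equal to or lower than the headline. If few subjects are affected, the two will nearly agree, and that agreement would support the headline.
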